5.4 Criteria for Initiation and Continuing of Trial Treatment

The lymphocyte count must be within normal limits before initiating treatment in Year 1, and at least 800/mm³ before initiating treatment in Year 2. If necessary, the treatment course in Year 2 can be delayed for up to 6 months to allow for recovery of lymphocytes. If this recovery takes more than 6 months, the subject will not receive the trial treatment anymore.

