Subjects who discontinue cladribine tablets at any time during the trial will continue to participate in the scheduled visits for assessments until his/her planned trial completion. In the event of early discontinuation from the trial, the subject should return for the Early Termination visit for final assessment.

For subjects who experience a relapse and initiated on another DMD (as per investigator's discretion), the subject will not participate further in any trial assessments and be followed-up by the investigator as standard of routine practice. The subject should however complete the early termination visit for final assessment.

Withdrawn subjects will not be replaced.

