6.5.1.4 Relapse Management

In case of neurological events related to multiple sclerosis, with relapse criteria met (Section 7.3.3), treatment with either acute short-term systemic corticosteroids or ACTH or plasma exchange can be administered at the discretion of the Investigator, following local good medical practice and international guidelines. The Investigator must complete the evaluation prior to treatment with steroids or other therapeutic intervention(s) that may alter the subject's neurological state.

Upon Investigator's judgement, any relapse that is considered severe should be treated and followed up as per standard of routine practice. In case of subject receiving treatment with any

other DMDs, the subject will be discontinued from the trial and will not undergo any trial related scheduled assessments; the subject should however complete the early termination visit for final assessment.

The initiation of second treatment course with Mavenclad[®] following acute management of relapse will be at investigator discretion.

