8.5 Description of Statistical Analyses

8.5.1 General Considerations

All analyses of all endpoints except the primary analysis, will be performed exploratively and, differences with a p-value of 0.05 or less will be considered nominally statistically significant.

Parameter estimates with associated 95% confidence intervals (CIs) will be reported in each analysis. No correction for multiple testing will be applied for any secondary or tertiary analysis.

Subjects' demographic factors and baseline clinical characteristics will be summarized with the following measures: mean with standard deviation, minimum and maximum for normally distributed continuous variables, median with interquartile range, minimum and maximum for other continuous variables and counts with percentages for categorical variables.

As the secondary and tertiary analysis set concerns repeated measurements of outcomes for each individual, it is likely that observations pertaining to each individual will be correlated. Furthermore, as this is a multi-center trial, it is likely that clustering of individuals within trial sites will produce an additional source of correlation. Mixed-effects regression, whereby a three-level hierarchical model is specified for observations within subjects within trial sites, will be used to account for within-subject and within-center correlation (Gibbons, 2010).

The parametric assumptions underlining the regression models specified will be examined. Should these assumptions be violated, alternative methods, such as non-parametric approaches, may be considered in addition.

Assessment Schedules

It is likely that the second year treatment may be delayed substantially due to grade 3 or 4 lymphopenia for a small number of subjects for whom the second dose is not required immediately. Due to the need for a finite follow-up period, a buffer of 3 months is given for subjects who do not receive the second treatment at the specified time. Subjects for whom treatment is delayed by over 3 months may not have all assessment data captured and as such, these observations will be treated as missing in efficacy analyses.

In each analysis, should assessment be delayed, subjects' assessment data will be treated as though it occurred at the time point specified and inferences will be conducted accordingly.

Missing Data

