- End = Start of study medication at or after the Month 12 Visit - 1 day, or if the subject did not receive Treatment Course 2: Start of study medication of Treatment Course 1 + 457 days (which is obtained by 360 (12 months) + 90 (3 months) + 7 (Visit window)) or date of discontinuation, if earlier.

Course 2 Treatment Period:

- Start = Start of study medication at or after the Month 12 Visit,
- End = End of Treatment Period.

Definition of Delayed Treatment Course 2

The Treatment Course 2 will be defined as delayed, if the start of study medication is delayed by more than 3 months (= 90 days) or did not start at all i.e.:

- Start of Study medication of Treatment Course 2 > Start of Study Medication of Treatment Course 1 + 457 days (which is obtained by 360 (12 months) + 90 (3 months) + 7 (Visit window)), or
- Treatment Course 2 never started (i.e., no study medication taken at or after the Month 12 Visit).

Data handling in case of a Delayed Treatment Course 2

For subjects with a Delayed Treatment Course 2, only data observed during the Course 1 Treatment Period will be analyzed in all efficacy analyses. Efficacy data after the Course 1 Treatment Period will be counted as missing in the statistical analyses and marked in the listings. In all efficacy analyses defined by Period, the subject will be classified as if the subject discontinued at the end of the Course 1 Treatment Period. For subjects without a delay the whole Treatment Period will be analyzed.

For all other analyses (except efficacy) the data is not limited to the Course 1 Treatment Period for subjects with a Delayed Treatment Course 2.

Definition of start of COVID-19-Pandemic

The start of COVID-19 pandemic will be defined by country as the earliest date of either the date of the first death from COVID-19 occurred in each country according to the published data by European Centre for Disease Prevention and Control on 26th June 2020 (<https://www.ecdc.europa.eu/en/publications-data/download-todays-datageographic-distribution-covid-19-cases-worldwide>) or 11th March 2020 (when the WHO declared COVID-19 pandemic).

Visit timing with respect to COVID-19 pandemic

A Visit is defined to be performed after the start of COVID-19 pandemic if the Visit end date is greater than the start of COVID-19 pandemic date.

Conversion factors

The following conversion factors will be used to convert days into months or years for all observations except Visit related dates:

- 1 month = 30.4375 days,

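### Year 2 efficacy estimates are conditional on a timely Course 2 start: observed later data from late starters and never-starters are set to missing, and no planned efficacy analysis keeps them

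*SAP*

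**What the plan says.** **SAP Section 9** classes Course 2 as delayed if it starts more than 457 days after Course 1 start, a figure "which is obtained by 360 (12 months) + 90 (3 months) + 7 (Visit window", or if "Treatment Course 2 never started (i.e., no study medication taken at or after the Month 12 Visit". For these subjects "only data observed during the Course 1 Treatment Period will be analyzed in all efficacy analyses". It adds: "Efficacy data after the Course 1 Treatment Period will be counted as missing in the statistical analyses and marked in the listings". In efficacy analyses by period they are handled as if they had left the study when the Course 1 Treatment Period ended. That period ends the day before Course 2 for late starters. For never-starters it ends 457 days after Course 1 start, or at discontinuation if earlier. Non-efficacy analyses are not truncated. SAP Section 7 lists the rule among the decisions made after the primary analysis.

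**The protocol** says the following:

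- Section 5.4: to allow lymphocyte recovery, "the treatment course in Year 2 can be delayed for up to 6 months".
- Section 5.5.1: "Subjects who discontinue cladribine tablets at any time during the trial will continue to participate in the scheduled visits for assessments". Section 5.5.2 repeats this.
- Section 8.5.1: "Subjects for whom treatment is delayed by over 3 months may not have all assessment data captured", and such observations are treated as missing for efficacy. Never-starters are not named.
- Section 6.5.1.4: starting Course 2 "following acute management of relapse will be at investigator discretion".

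**The concern.** Whether and when Course 2 starts is decided after baseline. It depends on lymphocyte recovery, on infection (protocol 5.5.1) and, after a relapse, on the investigator. A filter keyed to that event can make the removed data informatively missing, whereas the repeated-measures models assume missing at random and the NEDA and NEPAD regressions drop subjects of unknown status.

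The protocol's reason for missingness is that data may not have been captured. That does not cover data that were captured, and Section 5.5.1 requires visits to continue, so such data should exist.

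The affected results are the CUA, T1 Gd+ and T2 analyses over periods reaching into Year 2, Course 2 and Treatment Period ARR, 6-month confirmed disability progression, NEDA and NEPAD. The secondary endpoint is also exposed. Immune-cell counts to Month 24 sit in SAP Section 14, headed as efficacy, and the stated objective concerns repopulation. Subjects whose slow lymphocyte recovery delayed Course 2 would lose their later counts from that analysis.

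**Working it through.** **1. The cut-off.** 360 + 90 + 7 = 457, as stated. This is 457 - 360 = 97 days past the SAP's nominal year.

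**2. What a never-starter loses.** Start + 457 days is study day 458. On the SAP calendar (30-day months, counted here from Course 1 start), Month 15 is about day 450 and is nominally kept. Months 18 (540) and 24 (720) are lost. Days lost: 720 - 458 = 262, which is 262/360 = 73% of Year 2 and 262/720 = 36.4% of the two years. A late starter keeps everything up to the day before Course 2 and loses everything after it.

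**3. 0-24 month ARR.** The documents give neither the delayed share nor its outcomes, so these inputs are assumptions:

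- q = share affected, 5-20% (13 to 53 of the planned 265), all never-starters with complete follow-up
- 0.15 relapses per year in everyone else, and in affected subjects up to day 458
- k = rate ratio in affected subjects after day 458

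The planned analysis uses follow-up time as offset, so it returns 0.15. With all observed data the rate is 0.15 × [1 + q × 0.364 × (k - 1)]. The planned estimate divided by the all-data estimate is 1/[1 + 0.364 q (k - 1)]:

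| q | k = 0.5 | k = 1 | k = 1.5 | k = 2 | k = 3 |
|---|---|---|---|---|---|
| 5% | 1.009 | 1.000 | 0.991 | 0.982 | 0.965 |
| 10% | 1.019 | 1.000 | 0.982 | 0.965 | 0.932 |
| 20% | 1.038 | 1.000 | 0.965 | 0.932 | 0.873 |

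For k = 1.5-3 the understatement runs from 0.9% to 12.7%. At q = 10% and k = 2 it is 3.5% (0.150 against 0.155). At k = 0.5 the ARR is overstated by 0.9-3.8%.

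**4. A period lost entirely**, such as Month 18-24 imaging. The simple observed mean relative to the all-subject mean is 1/[(1 - q) + qk]. This is 0.976 to 0.714 for k = 1.5-3 and 1.026 to 1.111 for k = 0.5. These larger figures do not carry over to the 0-24 month ARR.

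**5. NEDA.** A delayed subject with a Course 1 event stays 'No'. An event-free one becomes 'Unknown': the study counts as not completed, and MRI status 'No' needs a Month 18 or Month 24 value. That subject is excluded even if a relapse was recorded later. Let d be the delayed share, p NEDA in retained subjects, e the share of delayed subjects with a Course 1 event, and q' their true NEDA. The planned estimate is (1 - d)p/[(1 - d) + de]; the all-subject value is (1 - d)p + dq'. With d = 10%, p = 0.5 and e = 0.4, the estimate is 0.45/0.94 = 0.479. The all-subject value is 0.450 if q' = 0 (+2.9 points) and 0.500 if q' = 0.5 (-2.1 points).

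**6. Disability progression.** In a never-starter, an EDSS rise first seen at Month 12 and confirmed at Month 18 loses its confirmation. The Month 6 and Month 12 scores are nominally 180 days apart, which meets the 166-day requirement, so the subject can be scored 'No' for progression.

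**7. Offsetting analyses.** None of the planned efficacy analyses keeps the removed data. TCS-2, used for yearly-period CUA change, also excludes delayed subjects.

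**The case against.** The strongest reply is that protocol 8.5.1 already prescribes missing handling for delays over 3 months, and that SAP Section 7 discloses the rule and improves on the protocol by keeping all Course 1 data. This stands for late starters. It does not cover never-starters, and it gives no reason for discarding captured data.

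Second, the effect may be small. Protocol 8.5.1 expects few subjects with a substantial delay and attributes it to lymphopenia, a drug effect. Subjects switched to another disease-modifying drug leave trial assessments after the Early Termination visit, so the rule removes little from them. Most of the named endpoints are tertiary and exploratory. This stands, and it favours the lower end of the illustrated range.

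Third, a reader might infer more than the documents support:

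- *That the Year 2 results are an on-treatment analysis of subjects who did well.* Delayed subjects stay in the FAS, and their Course 1 data enter the Treatment Period ARR, the repeated-measures models and NEDA. A single Course 2 tablet by the cut-off keeps all later data, whatever the compliance.
- *That the bias must favour the drug.* The calculations show either direction.
- *That the FAS almost duplicates TCS-2.* TCS-2 also requires at least 100% compliance in both courses, and it is not planned for ARR, NEDA or NEPAD. The SAP also tabulates delayed and not-started Course 2, and marks the removed values in listings.

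Fourth, simply lifting the filter is not enough. Year 2 visits are counted from the Month 12b visit and delayed assessments are analysed as if on time, so a late starter's Month 15 scan could be pooled with scans taken much sooner after baseline. Never-starters have no Course 2 Treatment Period in which to count relapses. This is correct, and the fix allows for it.

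**Conclusion.** The point holds in a limited form. Year 2 and 0-24 month efficacy estimates, and on a plain reading the later immune-cell counts, are conditional on a timely Course 2 start. The missingness this creates may be informative, and no planned efficacy analysis would show its effect.

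The size cannot be computed from the documents. Under the stated assumptions the 0-24 month ARR is understated by about 1-13%, and the sign reverses if removed subjects relapse less often than the rest. Not knowing the direction is a reason to analyse the observed data. The documents do not support calling the results selected on good outcome. The change should be made before the final analysis, but it does not bear on the Month 6 primary result or on safety.

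**What to change.** In SAP Sections 9 and 14:

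1. Add an FAS analysis of the Year 2 and 0-24 month efficacy endpoints and the immune-cell counts. Use every observed assessment and relapse to Month 24 or Early Termination, whatever the timing of Course 2, and treat only unobserved data as missing.
2. In that analysis, place late starters and never-starters by actual time since Course 1 start.
3. Define a Month 12-24 ARR so that never-starters contribute.
4. Report it beside the current rule, and label the current rule as conditional on timely Course 2 start. Confining the current rule to TCS-2 would do nothing, because that set contains no delayed subjects.
5. Reconcile the 3-month analysis cut-off with the 6-month delay the protocol permits, and say whether the rule applies to the immune-cell counts.

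Cost: SAP wording and some extra programming, mainly for the time anchoring. The protocol already requires the assessments. The added estimates mix follow-up with and without re-treatment and may be less favourable. Adding the analysis leaves the protocol 8.5.1 rule in place; replacing that rule would depart from the protocol.

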All derived lesion counts (except for the Mean T1 Gd+ lesion count) as specified below will be classified as NE if one of the components required for the calculation has been classified as NE by the central reading. The Mean T1 Gd+ lesion count will be set to NE only, if all T1 Gd+ lesion counts that correspond to the respective Period are classified as NE. In all other cases the mean will be calculated based on the available counts during the respective Period.

T1 Gd+ lesion count

- The T1 Gd+ are defined as follow: T1 Gd+ lesion count (by Visit) = T1 Gd+ lesions count from the MRI at the respective Visit.
- Mean T1 Gd+ lesion count (by Period) = sum of all T1 Gd+ lesion counts during the Period / # of scans belonging to the respective Period with non-missing T1 Gd+ lesion count.
All MRI scans belong to a Period that either have been performed during the Period including start and end. For post-Baseline periods starting at Baseline, the Baseline Visit will not be included. For example, Period 6.1 will include Month 1, 2, 3, 6 Visit, Period 24.1 will include all MRI scans except Screening and Baseline Visit).
- New T1 Gd+ lesion count (by Period) = number of new T1 Gd+ lesion counts from the comparison of the two selected MRI scans performed by central reading according to the Data Transfer Specification [8] (e.g. for Period 6.1 comparison of the MRI scans from Baseline Visit and Month 6 Visit will be performed)

Active T2 lesion count

As the active (i.e the new or enlarging) T2 lesion count depends on the length of the Period, it will be presented as reported (non-standardized) and annualized (standardized to 1 years (365.25 days)):

- Period length (days) = MRI date at end of Period – MRI date at start of Period +1,
- Annualized active T2 lesion count (by Period) = Total number of active T2 lesions per Period * 365.25/ Period length.

The following types of T2 lesions are defined per Period (standardized and non-standardized):

- Total new T2 lesion count =
Total number of new T2 lesions with T1 Gd+
+ Total number of new T2 lesions without T1 Gd+
- Total enlarging T2 lesion count =
Total number of enlarging T2 lesions with T1 Gd+
+ Total number of enlarging T2 lesions without T1 Gd+,
- Total active T2 lesion count =
Total new T2 lesion count
+ Total enlarging T2 lesion count

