Note: the number of new or enlarging T2 (with and without T1 Gd+) will be provided by central reading for each of the Periods including the Sequential Visit Periods, except for Period 3.1. For Period 3.1, the sum of the Sequential Visit Periods 100.1, 100.2 and 100.3 will be calculated.

For the calculation of the CUA lesion count, only T2 lesions that did not emerge from a T1 Gd+ lesion will be taken into account.

- Total active T2 lesion count (without T1 Gd+) =
Total new T2 lesion count without T1 Gd+
+ Total enlarging T2 lesion count without T1 Gd+

and will be standardized to the length of the Period (i.e. annualized). Total active T2 lesion count (without T1 Gd+) will only be calculated if T1 Gd+ counts for beginning and end of the corresponding Period are non-missing.

CUA lesion count

The number of CUA lesions for a Period will be defined as the sum of the T1 Gd+ and new or enlarging T2 counts for the respective Period and will be standardized to one scan (for T1) or one year (for T2) to harmonize the units of the 2 assessments.

$\#CUA(p_{\text{post-Baseline}})$ = Annualized CUA lesion count (by post-Baseline Period per 1 year)
= Mean T1 Gd+ lesion count (by Period i)
+ Annualized total active T2 lesion count (without T1 Gd+)
(by Period i per 1 year) Different from the primary analysis, T2

lesion count will be standardized to 1 year instead of 1 month due to longer periods and for comparison with other studies,

The CUA lesion count will only be calculated if both components (T1 and T2) are non-missing.

Data Handling in case of major PDs

PDs will not be considered in the planned statistical analyses (i.e., all data will be analyzed independent from any reported PD) except for PD due to MRI taken during steroid treatment (MRI will be excluded from the primary analysis).

Covariates and stratification factors

Age

Age (years) at time of Informed Consent (loaded from iRT). Missing age will be replaced as follows if used as a covariate:

- Age will be estimated from the year of birth (year of IC – year of birth), as recorded in the electronic Case Report Form (eCRF),
- If year of birth is missing, age will be imputed by the mean age of the FAS.

EDSS at Baseline

Expanded Disability Status Scale (EDSS) at Baseline will be categorized by:

- ≤ 3 (reference),
- >3 .

Missing EDSS at Baseline will be imputed by the median Baseline EDSS of the FAS if used as a stratification factor.

Pooled centers

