 - and any Lymphocyte count < 800 cells/mm³ at or after Month 12 Visit and before start of Treatment Course 2.
- Before or at / after Start of COVID-19 pandemic

The cumulative dose is defined as the sum of the number of tablets taken 10 mg divided by the weight for treatment year:

Cumulative dose = number of tablets taken in Treatment Course 1 * 10mg / weight in kg at Baseline + number of tablets taken in Treatment Course 2 * 10mg / weight in kg at Month 12b Visit.

The cumulative dose will be calculated only if the weight and number of tablets are available. Otherwise it will be missing. If the Treatment Course 2 wasn't started (i.e. no tablet taken in Treatment Course 2), the cumulative dose will be calculated only for the Treatment Course 1.

A subject data listing of the treatment compliance will be provided for the SAF.

14 Efficacy Analyses

The following sections describe the planned analyses for each of efficacy endpoints.

For the detailed definition of covariates and stratification factors that are used in the statistical models see Section 9. Details about the derived MRI endpoints and general handling of MRI data is described in Section 9 (“Data Handling of MRI data”).

Descriptive summary statistics will be presented for the absolute values and the changes from Baseline as applicable by Visit [Protocol Scheduled Visits except for Baseline (defined in Section 9)], or Period, for all efficacy endpoints (and the components, where applicable) for the FAS and respective subgroups or subsets for which the variables are analyzed. Details about the presentation of continuous and categorical variables are given in Section 9.

Wherever possible, all estimated results from the statistical models will be calculated with the same observed margin which reflects the population of the whole corresponding analysis set, regardless of missing data.

14.1 Primary Endpoints: Differences in the counts of CUA MRI lesions during the first 6 months compared to Baseline

The primary endpoints for the trial are defined as the differences in counts of CUA MRI lesions during the first 6 months compared to Baseline, i.e., the following differences will be evaluated:

1. Period of Month 1 to Month 6 compared to the Baseline Period.
2. Period of Month 2 to Month 6 compared to the Baseline Period.
3. Period of Month 3 to Month 6 compared to the Baseline Period.

For the detailed definition of Periods, please see Section 9 “Data Handling of MRI data”.

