Tertiary Endpoint: CUA lesion count > 0			
Tertiary (FAS)	Cross-tabulation for each post-Baseline Period: 
 • No: $\#\text{CUA}(p_{\text{post-Baseline}}) = 0$ • Yes: $\#\text{CUA}(p_{\text{post-Baseline}}) > 0$ vs Baseline Period: 
 • No: $\#\text{CUA}(p_0) = 0$ • Yes: $\#\text{CUA}(p_0) > 0$ 	McNemar Test.	Missing observations at Baseline: Subjects with a missing Baseline score will not be included in McNemar Test, however separate cross-tabulation table including missing/not-evaluable lesions counts will be presented and thus providing percentage related to all subjects. Missing post-Baseline observations: Same as above but adapted for missing post-Baseline observations (see "Missing observations at Baseline").
Tertiary (FAS by subgroup High-relapse activity)			
Tertiary (FAS by subgroup "Previous treatment with DMDs")			
ΔCUA = Difference in the annualized CUA lesion count between post-Baseline Periods and the Baseline Period $\#\text{CUA}$ = Annualized CUA lesion count during Periods			

Analysis (Analysis Set)	Derivation	Statistical Analysis Methods	Missing data handling
p ₀ = Baseline Period \$=Sequential Visit Periods			

Mixed-effects linear model for repeated measures

The change from Baseline in the annualized CUA lesion count by Period or Visit (i.e. the Sequential Visit Period) will be analyzed by a repeated mixed-effects linear model, which adjusts for the Baseline score (i.e. the annualized count), age (in years), EDSS at Baseline (≤ 3 , > 3), pooled center, Period /or Visit, within subject correlation and time between scans (in years), where applicable. An unstructured covariance matrix will be assumed for the model. If the model doesn't converge an alternative covariance structure will be used instead.

The estimated annualized CUA lesion count will be calculated based on the observed margin of the corresponding analysis set at Baseline.

Mixed-effects linear model

The change from Baseline in annualized CUA lesion count for each Period separately will be analyzed by a mixed-effects linear model, which adjusts for the Baseline score (i.e., the annualized count), age (in years), EDSS at Baseline (≤ 3 , > 3), pooled center, time between scans (in years) and within subject correlation. An unstructured covariance matrix will be assumed for the model. If the model doesn't converge an alternative covariance structure will be used instead.

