The estimated annualized CUA lesion count will be calculated based on the observed margin of the corresponding analysis set at Baseline.

Generalized linear model assuming negative binomial distribution

The annualized CUA lesion count will be evaluated using a generalized mixed-effects linear model with log link function assuming a negative binomial distribution. Period (i.e. Baseline Period, each post-Baseline Period as specified above) will be analyzed as: a) a repeated factor accounting for time between scans (in years) if the time is different between scans, or b) neglected, if the time between scans is constant (for example: for every 6 months Periods, 1 yearly Periods); and within subject correlation using an unstructured covariance matrix. Age and EDSS at Baseline (≤ 3 , > 3) will be used as fixed effect covariates.

The ratio of the annualized CUA lesion count of each post-Baseline Period versus the Baseline Period will be calculated as the inverse log of the difference of the estimated contrast between each post-Baseline Period and the Baseline Period.

Offset will be applied if needed.

The estimates, standard deviation and 95% confidence intervals for the annualized CUA lesion count at each Period and the ratio between Periods will be presented together with the estimated fixed effects. If the model doesn't converge an alternative covariance structure will be used instead of the unstructured covariance matrix.

The estimated annualized CUA lesion count will be calculated based on the observed margin of the corresponding analysis set at Baseline.

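### Tertiary MRI analyses: replacement values for time between scans in years are given in months, and annualized CUA adds a per-scan count to a per-year rate

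*SAP*

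**What the plan says.** **Covariate.** SAP Section 9 (MRI specific covariates) defines time between scans in years as the current scan date minus the previous visit's scan date, plus one day, divided by 365.25. The listed cases run from Month 1 to Month 24. If the preceding scan is missing, the replacement is 1 for Months 1, 2 and 3; 3 for Months 6, 15 and 18; and 6 for Months 12 and 24. For the visits they share, the values are the same as in the parallel list for months.

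**CUA.** For tertiary endpoints, Section 9 defines the Gd+ part as "sum of all T1 Gd+ lesion counts during the Period / # of scans belonging to the respective Period" with a non-missing count. To this it adds new or enlarging T2 lesions without T1 Gd+, multiplied by 365.25 and divided by Period length. The stated reason is that the parts "will be standardized to one scan (for T1) or one year (for T2) to harmonize the units of the 2 assessments".

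**Models (Section 14.3.1).** The by-visit linear model adjusts for time between scans. The text for the separate-Period linear model also adjusts for "pooled center, time between scans (in years) and within subject correlation", but the table row for the 2-year Period lists no such term, and the Month 1-12 and Month 1-24 row refers back to it. In the ratio model, Period is "a repeated factor accounting for time between scans (in years) if the time is different between scans" or "neglected, if the time between scans is constant (for example: for every 6 months Periods, 1 yearly Periods"). It adds: "Offset will be applied if needed". The ratio-model table rows list no window term.

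**LS means.** Section 14 says estimates "will be calculated with the same observed margin which reflects the population of the whole corresponding analysis set". Section 14.3.1 says: "The estimated annualized CUA lesion count will be calculated based on the observed margin of the corresponding analysis set at Baseline".

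**Windows.** The Screening and Baseline scans are at least 4 weeks apart (Protocol 5.2), and Baseline falls within 3 months of Screening, plus 7 days (Protocol 7). With the SAP's 30-day months that is 28 to 97 days. Post-Baseline windows run from one month to two years.

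**The concern.** A replacement value 12 times too large gives one subject extreme leverage on a covariate that otherwise varies by a few days. The affected estimates are T1 Gd+ by visit, MTR change at Month 24 and annualized brain volume change.

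The CUA problem is different. A mean count per scan does not depend on how long the window was; a yearly rate of non-enhancing T2 lesions does. In a longer window, more new lesions have stopped enhancing by the closing scan. They move out of the part that is not divided by time and into the annualized part. Baseline and post-Baseline windows differ by design, so a comparison can show change when disease activity is constant. By-visit CUA bears on onset of action, the trial's primary objective, so a Month 1 fall that is partly a window effect would be easy to misread.

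**Working it through.** **1. Replacement values.** Inputs: the Section 9 formula and its 30-day visit months.

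| Interval | (gap + 1)/365.25 | (gap + 1)/30.4375 | SAP value under years | SAP / years |
|---|---|---|---|---|
| 1 month | 31/365.25 = 0.085 | 1.02 | 1 | 11.8 |
| 3 months | 91/365.25 = 0.249 | 2.99 | 3 | 12.0 |
| 6 months | 181/365.25 = 0.496 | 5.95 | 6 | 12.1 |

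The listed values match the months formula.

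Leverage: a value of 6 instead of 0.5 adds 5.5² = 30.25 to the covariate's sum of squares. Take 265 subjects and 8 visits (2,120 intervals) and assume an interval SD of about 5.5 to 6.1 days. Ordinary variation then totals 0.49 to 0.59.

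- Eight-visit model: 30.25/(30.25 + 0.59) = 98%.
- Month 24 only (265 intervals, 0.06 to 0.07): 30.25/(30.25 + 0.07) = 99.8%.
- One Month 1-3 value of 1 instead of 1/12: (11/12)² = 0.84, a share of 59 to 63%.

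These are shares of covariate variation, not shifts in an estimate.

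Reach: the replacement applies only when the preceding scan is missing. CUA needs T1 Gd+ at both ends of the window, so CUA is then missing and the error cannot enter it.

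**2. Drift in CUA at constant activity.** Assumptions, none from the documents: r new lesions per month, T2 lesions persist, exponential enhancement with mean d months, and never-enhancing lesions at n times r. With L in months of 30.4375 days,

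E(L) = r{d + 12[1 − d(1 − e^(−L/d))/L + n]}.

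The first term does not depend on L. The enhancement part of the second is the average, over lesion ages 0 to L, of the probability of no longer enhancing. That average cannot fall as L grows, whatever the enhancement distribution.

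Example, d = 1, n = 0: E(31 days) = 5.47r, E(60) = 7.76r and E(183) = 11.01r. Month 1 against a 60-day Baseline is 5.47/7.76 = 0.705; six months is 11.01/7.76 = 1.42.

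| Inert drug, d = 0.5 / 1 / 2 months | n = 0 | n = 0.5 |
|---|---|---|
| Month 1 v 60-day Baseline | −23 / −30 / −28% | −14 / −17 / −14% |
| Month 1 v 91-day Baseline | −30 / −40 / −41% | −19 / −25 / −23% |

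Against a 28-day Baseline the change is +2 to +6%; against 31 days it is 0. Fixed rather than exponential durations span 0 to −86% for the 60-day Baseline.

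Period ratios against a 60-day Baseline, n = 0, depend on how T2 lesions without T1 Gd+ are identified:

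| Period, d = 0.5 / 1 / 2 | Judged at closing scan | Judged at any scan |
|---|---|---|
| Baseline-Month 6 | 1.21 / 1.42 / 1.60 | 0.94 / 0.94 / 0.97 |
| Baseline-Month 12 | 1.26 / 1.55 / 1.88 | 1.07 / 1.18 / 1.28 |
| Baseline-Month 24 | 1.29 / 1.61 / 2.04 | 1.11 / 1.24 / 1.35 |

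With d = 1, a true 50% fall over 12 months would show as 0.5 × 1.55 = 0.77 (−23%) or 0.5 × 1.18 = 0.59 (−41%).

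**3. By-visit model with the covariate.** Simulation with an inert drug: 265 subjects, mean 0.5 lesions/month (gamma shape 0.7), visits ±7 days, Baseline uniform over 28-97 days, 200 runs for each of the six d and n combinations; age, EDSS and centre omitted. Falls are counted in one direction (nominal 2.5%).

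| LS means evaluated at | Month 1 change per year | Nominal falls |
|---|---|---|
| Pooled interval (91 days) | −0.28 to +0.27 | 2-7% |
| Mean Baseline window | −0.30 to −0.68 | 10-20% |
| Month 1's own interval | −0.94 to −1.21 | 49-88% |

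Annualized total active T2 in the same runs stayed within −0.12 to +0.11 at every interval. If all Baseline windows were 28-42 days (an assumed range), the pooled interval would give +0.69 to +1.03 and so understate a real early fall.

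**4. Would a window term rescue the ratio models?** Baseline windows (28-97 days) and Periods (180 days or more) do not overlap. Fitting log E linearly over 28-97 days and extrapolating turns inert ratios of 1.13-1.60 at six months into 0.55-0.79, and 1.16-1.88 at one year into 0.14-0.44. A negative binomial simulation agreed in direction: 0.67-0.89 and 0.18-0.51.

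**The case against.** The strongest reply is that these analyses are exploratory (Protocol 8.5.1) and largely protected already. T2 counts are divided by Period length, the by-visit model adjusts for time between scans, and annualized total active T2, T1 Gd+ and new T1 Gd+ are reported separately. Section 10.1 summarizes Period lengths. The rule for classing a T2 lesion as without Gd+ sits in a review charter that is not available here. If the non-enhancing share did not depend on window length, CUA would be nearly flat: 6.78 to 6.98 per year from 28 to 720 days, at 12 lesions per year with 30-day enhancement and a share of one half.

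Much of this stands. It limits the point to tertiary results and makes the size conditional. It does not remove the unit error. Nor does it settle the LS-mean interval: the common margin in Section 14 favours a pooled interval, but none is named, and the listed covariate cases give no Baseline value. Annualized total active T2 is not listed for Months 1-12 and 1-24, and nothing marks it as the check on CUA.

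Three stronger inferences are not supported:

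- That the covariate was meant to absorb the CUA drift. The SAP says only that models account for time between scans; division by Period length is its stated adjustment. The general rule could also be extended to Baseline minus Screening, although no such case is listed.
- That the replacement error corrupts CUA. It cannot, as shown above.
- That a mandatory window term or offset is the remedy. The term creates false falls. The annualized counts are already divided by Period length, and Section 14.1.2 declines an offset for that reason. In a single-Period model, the Period's own length would still not bring in the Baseline window.

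**Conclusion.** The point holds for tertiary analyses.

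- **Replacement values:** wrong as written, about 12-fold, with no assumption needed. The effect on any T1 Gd+, MTR or brain-volume estimate depends on how many values are replaced and was not estimated.
- **CUA:** the sum does not put its parts on one scale. The by-visit direction needs only constant lesion activity and persistent T2 lesions. The sizes rest on assumed enhancement durations. For Periods the sign also depends on the unseen reading rule: the inert six-month ratio runs from 0.94 to 1.60 against a 60-day Baseline with n = 0.
- **Ratio-model exemption:** calling the interval constant for 6-month and yearly Periods overlooks a Baseline comparator of 28 to 97 days.

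A reader might infer that the by-visit model will produce a false early fall. That depends on the LS-mean interval. A pooled interval showed no systematic false fall over the full Baseline range, while Month 1's own interval did. The completed primary analysis does not use the annualized measure or the covariate in years, and no finding is made about it.

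**What to change.** 1. In SAP Section 9, replace 1, 3 and 6 under the years heading with 1/12, 3/12 and 6/12.
2. State one time-between-scans value for the by-visit LS means. No value is neutral for every Baseline window, so it should be fixed before the final results are seen. Reconcile the model text in Section 14.3.1 with its table rows.
3. Do not add a linear window-length term or an offset to the Period ratio models. Say so in place of the conditional wording.
4. Keep the CUA definition (Protocol 7.3.1.2) and the completed primary analysis. Present annualized total active T2 (Section 14.3.7) beside each by-visit and Period CUA result as the measure on a single time scale. Add it for Months 1-12 and 1-24; Section 9 says central reading supplies those counts.
5. Add a caution, beside the Period-length summary in Section 10.1, that CUA comparisons across windows of different length may partly reflect window length.

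The cost is SAP wording, one programming correction, T2 models for two more Periods and a little tabulation. No new MRI reading is needed.
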